		
alcohol use.
 
Subject will be screened for the following STIs during the enrolment visit: HIV, syphilis, hepatitis A/B/C, Chlamydia trachomatis, Neisseria gonorrhoea, and Mycoplasma genitalium.
 
Participants will be asked to return approximately one week later to discuss their HIV result and whether they wish to proceed with initiation of PrEP.
 
The decision regarding initiation of continuous or intermittent PrEP is based on a discussion with the subject and study team (doctor/nurse), subjects' personal preference, medical considerations and whether the expected use will surpass more than 15-20 tablets of FTC/TDF per month.
 
HIV testing will be repeated at 2, 4 and 8 weeks from the most recent high risk exposure (for HIV acquisition) prior to initiation of PrEP. Thereafter participants are requested to visit the clinic every 3 months from PrEP initiation (for the next 24 months) for HIV & STI testing, evaluation of compliance (blood test for drug monitoring in continuous PrEP arm, drug diaries in both continuous and intermittent PrEP arms), assessment of clinical and/or biochemical adverse reactions and quality of life and sexual behaviour assessment. Subjects will be asked to answer the same questions regarding sexual behaviour and quality of life at follow up visits as at inclusion study visit.

Statistics	Sample size	Not applicable
	Methods	Categorical variables will be described by means of absolute and relative frequencies, while continuous variables by means of mean, standard deviation, quartiles, min and max.

LIST OF ABBREVIATIONS

AE	Adverse Event
ART	Anti retroviral therapy
COHP	Country of high prevalence of HIV
CRA	Clinical Research Associate
CRF	Case Report Form
CSR	Clinical Study Report
CT	Chlamydia trachomatis
DM	Data Manager
EC	Ethics Committee
eCRF	Electronic Case Report Form
EDC	Electronic Data Capture
EMA	The European Medicines Agency
GCP	Good Clinical Practice
HIV	Human Immunodeficiency Virus
ICF	Informed Consent Form
ICH	International Conference on Harmonisation
IMP	Investigational Medicinal Product
ISF	Investigator Site File
ITT	Intention-To-Treat
MG	Mycoplasma genitalium
MSM	Men who have sex with men
NG	Neisseria gonorrhoea
PI	Principal Investigator
PIS	Patient Information Sheet
PrEP	Pre-Exposure Prophylaxis
SAE	Serious Adverse Event
SD	Standard Deviation
SDV	Source Data Verification
SUSAR	Suspected Unexpected Serious Adverse Reaction
STI	Sexually Transmitted Infections

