Drug resistance is an important factor in HIV treatment. Usually HIV drug resistance occurs in an individual as a result of poor adherence to ART. Alternatively, HIV drug resistance may be acquired at the time of transmission if infected by a person already harbouring a resistant virus, i.e. transmitted drug resistance. On a worldwide basis, three cases of HIV seroconversions despite good PrEP adherence have been reported [Knox D et al. 2016]. In one case, the PrEP user was infected by a virus resistant to tenofovir + emtricitabine. According to national surveillance data for drug resistance among newly diagnosed patients in Norway, the frequency of tenofovir and/or emtricitabine resistance is low: in 2015, two of the 149 samples tested were resistant to emtricitabine (1%), and none to tenofovir

In existing guidelines in Europe and US, there is a consensus that PrEP should be made available for those at highest risk of HIV infection. This particularly includes men who have sex with men (MSM) and male to female transgender persons, based on the incidence of HIV infection, individual risk behaviour and other factors affecting sexual behaviour.

The World Health Organization (WHO)'s guidelines for PrEP (from 2015) identify populations with a HIV infection incidence of 3 per 100 persons/ year. These include sub-populations of MSM, male to female transgender persons and heterosexuals with a HIV positive partner not virologically suppressed. The risk will vary and will be evaluated in each individual case.

The European AIDS Clinical Society (EACS) guidelines recommend that PrEP should be considered for HIV negative MSM and transgender persons who are inconsistent in their use of condoms when having sex with casual partners or HIV positive partners who are not on treatment. Centre for Disease Control and Prevention (CDC) in US recommend PrEP to MSM with high risk of HIV infection, based on individual risk. As in several other countries, e.g. the United Kingdom, The Netherlands and France, the Norwegian Associations for Infectious

Diseases has settled on a similar definition of risk and recommend PrEP to the similar target populations in its guidelines.

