2 OBJECTIVES

This study is designed to evaluate implementation of PrEP treatment as a part of the general HIV preventive program in Norway. The target groups are mainly MSM and transgender persons at high risk of HIV infection, as well as other subjects at risk of HIV infection due to their sexual practices.

Objectives include assessment of the following:

- Assess the impact of PrEP on the sexual and psychological health of PrEP users
- Incidence of sexually transmitted infections (STIs) in PrEP users compared to those not taking PrEP
- Assessment of drug compliance
- Incidence of HIV seroconversion despite PrEP
- Frequency and development of drug resistance in subjects who HIV-seroconvert (if any)

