3 POPULATION

3.1 Inclusion Criteria

In order to participate in the PrEP arm of this study the subjects must meet all of the following inclusion criteria:

1. Male, female or transgender persons aged ≥ 18 years who are offered or have started PrEP in routine clinical practice, and 2, 3, 4, 5, 6 or 7 (below).
2. Men who have sex with men (MSM) and transgender persons;
 - a. who have had unprotected anal sex with two or more partners during the last six months and/or
 - b. who have had bacterial sexually transmittable infection(s) during the last twelve months and/or
 - c. who have used post-exposure prophylaxis(PEP) during the last twelve months and/or
 - d. who use recreational drugs when having sex
3. Indication for PrEP is present according to the assessment of the health care provider
4. Men and women who are at high risk of HIV according to their sexual practices
5. HIV-negative partner of a HIV-positive person not yet virologically suppressed by antiretroviral therapy (ART)
6. Sex workers with inconsistent condom use
7. Persons with inconsistent condom use with sexual partners in / from countries with a high prevalence of HIV (COHP)

Subjects who are included in the PrEP arm will act as their own controls regarding possible changes in psychological and sexual health. At the screening visit they will complete questionnaire requesting information related to last 6 months prior to study start. Individuals who seroconvert during the observational period will be transferred to the out-patient clinic for Infectious Diseases as is already standard of care.

Patients diagnosed with HIV in general clinical practice and referred to the out-patient clinic at the Dept. of Infectious Diseases, OUS, will be asked to act as controls to assess their past psychological and sexual health. They will be asked to sign the consent form and answer the same questionnaire as those in the PrEP arm but not followed further in this study.

Frequency of STI reported to the National Institute of Public Health (MSIS) will be compared with the frequency of STIs in the study cohort.

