3.2 Exclusion Criteria

In order to participate in the study subjects must not meet any of the following exclusion criteria:

1. HIV positive subjects
2. Subjects who cannot take FTC/TDF due to contraindications

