3.3 Control Group

Subject to be included in the control group:

1. Enrolled patients will be regarded as their own control when it comes to their sexual health and quality of life reported for period prior to inclusion in the study.
2. Subjects newly diagnosed with HIV in general clinical practice and referred to the out-patient clinic at the Dept. of Infectious Diseases, OUS, who meet the following inclusion and exclusion criteria:
 - a. Inclusion criteria in the control group:
 - i. Confirmed positive HIV-test, AND
 1. Confirmed negative HIV-test < 12 months ago, OR
 2. Self-reported assumed time of infection < 12 months ago, AND
 - ii. Resident for > 6 months in a country of one of the following regions (EU/EFTA, North America or Australia/New Zealand) at the time of confirmed or assumed infection.
 - b. Exclusion criteria in the control group:
 - i. Confirmed positive HIV-test > 12 months ago, OR
 - ii. Self-reported assumes time of infection > 12 months ago.
3. Frequency of STI reported to the National Institute of Public Health (MSIS) will be compared with the frequency of STIs in the study cohort.

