### **3.3 Control Group**

Subject to be included in the control group:

1. Enrolled patients will be regarded as their own control when it comes to their sexual health and quality of life reported for period prior to inclusion in the study.
2. Subjects diagnosed with HIV in general clinical practice and referred to the out-patient clinic at the Dept. of Infectious Diseases, OUS.
3. Frequency of STI reported to the National Institute of Public Health (MSIS) will be compared with the frequency of STIs in the study cohort.

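### The only external control group the study recruits is selected on having acquired HIV, so it cannot serve as a control for the effect of PrEP on sexual and psychological health

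*Protocol*

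**What the plan says.** The protocol has three comparators (section 3.3): the PrEP users' own period before inclusion, a recruited group with HIV, and national STI surveillance (MSIS). Only the second is a group of other people whom the study recruits.

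- **Who they are.** Protocol 3.3 item 2 takes "Subjects newly diagnosed with HIV in general clinical practice and referred to the out-patient clinic at the Dept. of Infectious Diseases, OUS, who meet the" criteria set out there. The first of these reads "Confirmed positive HIV-test, AND" then asks for infection within the past 12 months and a residence condition. Not having used PrEP is not among the criteria. SAP 3.3 is looser: "Subjects diagnosed with HIV in general clinical practice and referred to the out-patient clinic at the Dept. of Infectious Diseases, OUS", with no limit on recency or residence.
- **What they are for.** Protocol 3.1 says that they "will be asked to act as controls to assess their past psychological and sexual health". They complete the PrEP arm's questionnaire once and are not followed.
- **Who is in the PrEP arm.** Protocol 3.2 excludes "HIV positive subjects". Section 3.1 criterion 2 admits MSM and transgender persons through markers of risk: condomless anal sex with at least two partners, a recent bacterial STI, recent PEP, or drug use during sex.
- **What is analysed.** Section 7.2 of both documents covers only participants on PrEP, and 7.3 is descriptive. Neither mentions the HIV-diagnosed group or says what it may be compared with.

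**The concern.** The first objective, which section 1.1 also makes the main one, asks what PrEP does to users' sexual and psychological health. An external control for that question should show how comparable people fare without PrEP, which means HIV-negative people at similar risk who do not take it. The recruited group consists instead of people who became infected. Infection risk depends on the very things the questionnaire measures: partners, condom use, STI history and drug use. People with more of these enter the control group more often.

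This is separate from differences in risk-group mix, earlier PrEP use or recall. It would remain if every control were an MSM meeting criterion 2 who had never taken PrEP and remembered perfectly. A larger group, or adjustment for eligibility category, would not remove it. What is at stake is the conclusion: two columns of frequencies headed PrEP arm and control invite a reading as an effect of PrEP, and nothing in either document rules that reading out.

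**Working it through.** The plan gives no sample size, power or effect figure to reproduce. The outline marks sample size as not applicable. The check illustrates what selection on infection does.

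**Inputs.** From the documents: Protocol section 1 says that the cited WHO guideline serves to "identify populations with a HIV infection incidence of 3 per 100 persons/ year". Assumed, because the documents give no values: *p*, the prevalence of a risk factor among eligible non-users; *k*, its hazard ratio for HIV; the coefficient of variation (CV) of partner numbers; and *q*, the factor's prevalence in the PrEP arm.

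**Step 1. Who can enter the group.** At 3 per 100 person-years, 12-month risk = 1 − exp(−0.03) = 0.0296, about 3%. About 97 of 100 comparable untreated people would not qualify in a given year. This shows how selective the definition is; it does not measure bias.

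**Step 2. Prevalence of a risk factor among the infected.** With infection uncommon in the period, prevalence = *pk* / (*pk* + 1 − *p*).

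| *p* | *k* | Calculation | Among infected | Excess over *p* |
|---|---|---|---|---|
| 40% | 1.25 | 0.50 / 1.10 | 45.5% | 5.5 points |
| 40% | 2 | 0.80 / 1.40 | 57.1% | 17.1 points |
| 40% | 3 | 1.20 / 1.80 | 66.7% | 26.7 points |
| 60% | 1.25 | 0.75 / 1.15 | 65.2% | 5.2 points |
| 60% | 2 | 1.20 / 1.60 | 75.0% | 15.0 points |
| 60% | 3 | 1.80 / 2.20 | 81.8% | 21.8 points |
| 80% | 2 | 1.60 / 1.80 | 88.9% | 8.9 points |
| 80% | 3 | 2.40 / 2.60 | 92.3% | 12.3 points |

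For *p* of 40-60% and *k* of 2-3, the controls show 57-82%, an excess of 15-27 points.

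**Step 3. A count such as number of partners.** If hazard is proportional to the count, the mean among the infected is (1 + CV²) times the mean among eligible non-users: 1.25 times at CV 0.5 and 2 times at CV 1.0.

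**Step 4. Does this fix the sign of the observed difference?** Take *p* = 20% and *k* = 2. The controls then show 0.40 / 1.20 = 33.3%.

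- PrEP arm at *q* = 20%: observed difference 20 − 33.3 = −13.3 points; against eligible non-users it would be 0.
- PrEP arm at *q* = 50%: observed difference 50 − 33.3 = +16.7 points; against eligible non-users it would be +30.

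The shift is 13.3 points in both cases, but the observed sign differs. Because criterion 2 selects the PrEP arm on risk, the second case is quite possible.

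**The case against.** The strongest reply is that no contrast with this group is specified. Section 7.2 limits the description to people on PrEP, change is to be judged within participants, and Protocol 3.4 explains the control criteria in terms close to a descriptive purpose: recent infections among residents of places where PrEP may have been obtainable. The sizes above also rest on assumed inputs, and the 3 per 100 figure identifies guideline target populations; it is not an incidence for this cohort. All of that stands. The bias arises only if the comparison is made. But the plan calls these people controls for the subject of the main objective, gives them the PrEP arm's questionnaire and never says the group is descriptive only.

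Three stronger readings are tempting, and the documents do not support them.

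- *Every contrast will make PrEP users look lower risk.* Step 4 shows otherwise. Only this component of bias has a predictable direction, and only for factors that raise HIV risk. None is derived for psychological health.
- *This group stands for non-users in the STI objective* ("Incidence of sexually transmitted infections (STIs) in PrEP users compared to those not taking PrEP"). The documents never say so. They name MSIS for STI frequency, and one questionnaire without follow-up cannot give incidence.
- *The group could hide a real rise in risk behaviour on PrEP.* It cannot hide a within-person change, which is assessed against participants' own earlier answers.

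**Conclusion.** The point holds in a limited form. The HIV-diagnosed group is selected on the outcome PrEP prevents, so it cannot act as a control for the effect of PrEP on sexual and psychological health. For factors that raise HIV risk, the selection moves the contrast toward PrEP users appearing lower risk than they would against eligible non-users. The move is 15-27 points at an assumed prevalence of 40-60% and hazard ratio of 2-3, and about 5 points at a ratio of 1.25. The direction needs only a ratio above 1; the size depends on assumptions that the documents cannot settle. The own-control analysis and the MSIS comparison are not affected by this selection.

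**What to change.** In Protocol 3.1, 3.3 item 2 and 3.4, and the matching SAP text:

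1. Stop calling this group a control for the effect of PrEP. Describe it as a series of people recently infected in settings where PrEP could have been available, using the same recency and residence limits in both documents.
2. Report the proportion who met inclusion criteria 2-7 before infection, with a 95% interval. Criterion 3 depends on a provider's judgement, so say how it will be handled in retrospect. Add the series to section 7.2, which at present covers only participants on PrEP.
3. State that no difference between this series and the PrEP arm will be reported as an effect of PrEP, and that objective 1 rests on the own-control comparison already planned.
4. Optionally, tabulate the Visit 0 questionnaire and STI screen of consented, eligible participants who do not start PrEP. The outline (Methods & procedures) has participants return to discuss "whether they wish to proceed with initiation of PrEP", so such people may exist. This also needs an exception in 7.2. Label it a baseline description: the group may be small and self-selected, and it gives neither an effect of PrEP nor STI incidence.

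The cost is wording and one or two descriptive tables, with no new patients, visits or tests. The downside is that the study gives up an external comparison for objective 1.

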5.4 Duration of Treatment

Subject will be followed up for a period of up to 24 months.

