7.3 Descriptive statistics

Categorical variables will be described by means of absolute and relative frequencies, while continuous variables by means of mean, standard deviation, quartiles, min and max. Analyses will consider data collected at variable observational points, according to clinical practice and clinical judgement. In order to summarize data by time point the nearest available evaluation measurement will be considered (acceptable range).

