## 7 STATISTICAL METHODOLOGY AND DATA MANAGEMENT

### 7.1 Statistical Analysis Plan

All analyses will be performed by the Sponsor after the study is completed and the database is locked. Statistical programming and analyses will be performed using SAS and/or other validated statistical programs. A detailed statistical analysis plan (SAP) will be described in a separated document.

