### **7.3 Descriptive statistics**

Categorical variables will be described by means of absolute and relative frequencies, while continuous variables by means of mean, standard deviation, quartiles, min and max. Analyses will consider data collected at variable observational points, according to clinical practice and clinical judgement. In order to summarize data by time point the nearest available evaluation measurement will be considered (acceptable range).

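### Two objectives ask for incidence, but the plan gives only frequencies without person-time, and its only named STI comparator, MSIS reports, would tend to show an excess without any PrEP effect

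*Protocol*

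**What the plan says.** Section 2 of both documents lists "Incidence of sexually transmitted infections (STIs) in PrEP users compared to those not taking PrEP" and "Incidence of HIV seroconversion despite PrEP" among the objectives. The only summaries planned are in section 7.3, again in both: "Categorical variables will be described by means of absolute and relative frequencies", with the usual moments and quartiles for continuous variables. By-time-point tables take the nearest available evaluation. No rate, person-time, confidence interval or repeat-infection rule is stated. Section 7.1 adds "A detailed statistical analysis plan (SAP) will be described in a separated document".

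Observation time varies: "Subject will be followed up for a period of up to 24 months" (Protocol 5.4). Protocol 4.1 admits people who have already started PrEP and provides for collecting their history back to that start.

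Protocol 3.3 names three controls. Enrolled subjects act as their own controls for sexual health and quality of life. Newly diagnosed HIV patients complete a questionnaire once. The third item is the only one that names STI frequency: "Frequency of STI reported to the National Institute of Public Health (MSIS) will be compared with the frequency of STIs in the study cohort". The SAP file repeats it.

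For HIV, Protocol 3.5 records a positive result during PrEP use as a PrEP failure. Protocol 4.1 gives 12 weeks as the window for ruling out infection. Protocol 4.2 says the tests at weeks 2, 4 and 8 are meant to find people already seroconverting when they join.

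**The concern.** An incidence needs a time base. When subjects are followed for different lengths, the percentage ever infected depends on how long they were watched as well as on their risk. It cannot be read as an incidence or compared with an outside figure.

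The STI objective also needs a group not taking PrEP. MSIS holds reported cases from everyone, PrEP users included, and the protocol outline says people who decline the study are still offered PrEP. The Introduction says the number of sexually active MSM in Norway is unknown, so no risk-matched denominator is available from the documents. The cohort enters because of high risk, with a bacterial STI in the past year as one route, and is screened about every 3 months. Both features raise its STI count relative to notifications whether or not PrEP changes behaviour. The Introduction calls the effect of PrEP on STI incidence important, so a misleading contrast matters.

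For HIV the events may be few. An infection acquired before PrEP but first detected on it would be counted as occurring despite PrEP, and one such case can change the result.

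**Working it through.** The plan gives no sample size, event count or rate for these objectives (the outline says sample size is not applicable), so there is no figure to reproduce. All rates, numbers of subjects and durations below are assumptions unless a source is named.

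**1. STI time base.** With constant rate r per person-year and follow-up t, the share with at least one STI is 1 − exp(−r·t).

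| r | 0.5 y | 1 y | 2 y |
|---|---|---|---|
| 0.3 | 14% | 26% | 45% |
| 0.6 | 26% | 45% | 70% |
| 1.0 | 39% | 63% | 86% |

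Each row has one underlying rate. A single 3-month round at r = 0.6 gives 1 − exp(−0.15) = 14% whatever the total follow-up, so by-visit tables are far less affected.

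**2. HIV time base.** Take 2 seroconversions. The exact Poisson limits for 2 events are 0.242 and 7.225.

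| Subjects | Percentage | Mean follow-up | Person-years | Rate per 100 PY (95% CI) |
|---|---|---|---|---|
| 500 | 0.4% | 0.5 y | 250 | 0.80 (0.10–2.89) |
| 500 | 0.4% | 1 y | 500 | 0.40 (0.05–1.44) |
| 500 | 0.4% | 2 y | 1000 | 0.20 (0.02–0.72) |

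With 300 subjects the percentage is 0.67% throughout and the rate is 1.33, 0.67 or 0.33.

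**3. Are HIV events likely to be few?** The Introduction cites a population incidence of 3 per 100 per year and 86% protection. If both applied here, the rate would be 3 × (1 − 0.86) = 0.42 per 100 PY. That is 0.42 expected events in 100 PY and 4.2 in 1000 PY.

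**4. One infection present at inclusion.** Suppose one of the 2 events among 500 was already present at entry and all 500 start PrEP in the study. Leaving out that event and the first 12 weeks removes 500 × 12/52 = 115 PY:

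- 0.5 y: 1/135 = 0.74 per 100 PY, against 0.80.
- 1 y: 1/385 = 0.26, against 0.40.
- 2 y: 1/885 = 0.11, against 0.20.

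**5. Direction of the MSIS contrast.** Let s be the share of infections that are symptomatic and always found, D the mean duration of the rest, and T the testing interval. The share found is s + (1 − s)(D/T)(1 − exp(−T/D)). For s = 0.3 and D = 0.5 y this is 0.85 at 3 months, 0.74 at 6 months and 0.60 at 12 months. Quarterly testing then finds 1.15 or 1.41 times as many infections at the same true incidence. Over s = 0.1–0.5 and D = 3–12 months the ratio is 1.05–1.37 against 6-monthly testing and 1.15–2.08 against yearly testing.

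For selection, let individual rates follow a gamma distribution with mean μ and shape k, and require at least one STI in the past year. With b = k/μ and p0 = (b/(b+1))^k, the expected rate is (μ − p0·k/(b+1))/(1 − p0). For μ = 0.2 and k = 1 this is 0.37, or 1.8 times the mean. Over μ = 0.1–0.5 and k = 0.5–2 the ratio is 1.4–2.8, for subjects who qualify by that route only.

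Both ratios exceed 1 with no PrEP effect. The inputs are not in the documents, so only the sign carries over.

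**The case against.** The study is descriptive, its main aim is psychological and sexual health, and a separate detailed SAP is promised. That SAP may settle all of this. It was not supplied, and the file labelled SAP is another version of the protocol with the same section 7, so its agreement adds no independent support. A rate with an interval is itself descriptive, so the study's purpose is no reason to omit it.

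By-visit percentages are planned and largely avoid the follow-up problem. That stands, and limits the time-base point to cumulative figures.

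Own-control data and the questionnaire given to the newly diagnosed HIV patients may include STI history. No STI comparison based on them is stated, recalled history is not equivalent to serial screening, and those patients were chosen for having acquired HIV.

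The documents do not describe the testing behind MSIS reports. The bias is therefore inferred from the cohort side, its lower end is close to none, and PrEP users inside MSIS would dilute the contrast.

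A reader might infer that the plan has no rule for HIV infections present at entry, or that 3.2 and 7.2 would drop them. The documents do not support this. Protocol 3.5 registers any positive during PrEP use as a failure, and 7.2 removes people who fail inclusion criteria, whereas HIV positivity is an exclusion criterion. Provirus testing after recent exposure also covers part of the problem. A reader might also infer that PrEP time before enrolment will enter the denominator. No section says so.

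**Conclusion.** The point holds for the supplied documents. The stated summaries do not deliver the two incidence objectives, and the MSIS comparison does not contrast PrEP users with people not taking PrEP. Under the assumed rates, one underlying STI risk can appear as a cumulative percentage that differs nearly threefold (26% to 70%), and one HIV percentage can stand for rates that differ fourfold (0.80 to 0.20 per 100 PY).

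It would go too far to conclude that a higher STI frequency than in MSIS would be wholly artefact, or to correct for it by a factor. The documents support a likely apparent excess from testing and selection; they give nothing from which to size it. On HIV, the plan's rule is usable as the main count. What is missing is a display of how far the result depends on infections already present at inclusion. The collected data remain usable, and the defect lies in the stated analysis.

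**What to change.** Amend 7.3 and 3.3, or put the following in the separate SAP.

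1. **Rates.** Report HIV seroconversions and each STI per 100 person-years, using all visits including Extra visits. Use an exact Poisson 95% interval for HIV and a robust or negative-binomial interval for recurrent STIs.
2. **Risk time.** Start at PrEP start, or at enrolment for people already on PrEP, and show history from before enrolment separately. End STI time at the last STI test on PrEP. End HIV time at the first positive or last HIV test on PrEP. After a recorded stop, include the first later HIV test and the time up to it in the main rate, so that infections acquired on PrEP but found just afterwards are not lost. Add a sensitivity analysis that ends at the stop.
3. **STI counting.** Report Visit 0 infections separately. State a repeat-infection rule, for example a new positive after recorded treatment and at least 30 days, with 14 and 60 days as sensitivity analyses.
4. **HIV at inclusion.** Keep all positives on PrEP as the main rate, in line with 3.5. Add a sensitivity rate without seroconversions first found within the protocol's 12-week window after PrEP start, removing that risk time too and using provirus results where available. The outline dates the early tests from the last high-risk exposure and 4.1 dates them from PrEP start; these passages must be reconciled.
5. **MSIS.** Present it as calendar-time context for organisms both sources record, beside the cohort's test counts and positivity. State that it is not restricted to non-users and does not estimate a PrEP effect.

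The cost is wording and modest programming, since test results, PrEP use and medication dates are already planned data. The downsides are that the STI comparison becomes descriptive, the repeat rule may count some persistent infections as new, and the HIV sensitivity rate may leave out some true early failures.
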